# Non-haematological toxicity

Table. Olaparib non-haematological toxicity management guidelines

Table. Olaparib non-haematological toxicity management guidelines		
Toxicity	Action	
Any non-haematological	First occurrence	
toxicity Grade ≥3	
 
Withhold dose for up to 28 days until recovery to Grade ≤1. For Grade 3 toxicity olaparib may be resumed at the same dose level at the discretion of the Investigator. In the case of Grade 4 toxicity olaparib should be reduced to the first dose reduction level for non-haematological toxicity.
 
If symptoms do not recover to Grade ≤1 (or recover to baseline level if baseline was Grade 2) within 28 days, discontinue olaparib. Patients with alopecia may continue on trial treatment.
 
Second occurrence
 
Withhold dose for up to 28 days until recovery to Grade ≤1 then reduce olaparib to the next dose reduction level for non-haematological toxicity.
 
If symptoms do not recover to Grade ≤1 (or recover to baseline level if baseline was Grade 2) within 28 days, discontinue olaparib. Patients with alopecia may continue on therapy.
 
Third occurrence
 
Withhold dose for up to 28 days until recovery to Grade ≤1 then reduce olaparib to the second dose reduction level for non-haematological toxicity. Patients who are currently receiving the second dose reduction level should discontinue olaparib.
 
	

Toxicity	Action	
	
 
If symptoms do not recover to Grade ≤1 (or recover to baseline level if baseline was Grade 2) within 28 days, discontinue olaparib. Patients with alopecia may continue on therapy.
 
Fourth occurrence
 
	
	Discontinue olaparib.	
New or worsening pulmonary symptoms  NB. Pneumonitis is an	If new or worsening pulmonary symptoms (e.g. dyspnoea) or radiological abnormalities occur in the absence of a clear diagnosis, an interruption in trial treatment dosing is recommended and further diagnostic workup (including a high resolution CT scan) should be performed to exclude pneumonitis.	
important potential risk for olaparib	
 
The following assessments, and additional assessments if required, should be performed to enhance the investigation and diagnosis of potential cases of pneumonitis:         
 
Physical examination and signs and symptoms (cough, shortness of breath and pyrexia, etc.) including auscultation for lung field.
 
Saturation of peripheral oxygen (SpO2)
 
The following markers should be measured where possible: ILD markers
 
 
 
	
	
 
(KL-6, SP-D) and β-D-glucan; tumour markers related to disease progression.
 
Following investigation, if no evidence of abnormality is observed on CT imaging and symptoms resolve, then trial treatment can be restarted, if deemed appropriate by the Investigator.
 
If significant pulmonary abnormalities are identified, these should be raised
 
	
	
 
with the PHOENIX Trial Team in the first instance for discussion with the Chief or Coordinating Investigator.
 
If Grade ≥2 pneumonitis is confirmed, olaparib treatment should be discontinued and the patient treated appropriately.
 
Any event of pneumonitis should be reported as an AESI, please refer to Section 16 for further information.
 
	
Nausea and vomiting	
 
Events of nausea and vomiting are known to be associated with olaparib treatment. They are generally mild to moderate (Grade ≤2) severity, intermittent and manageable on continued treatment. The first onset generally occurs in the first month of treatment for nausea and within the first 6 months of treatment for vomiting. For nausea, the incidence generally plateaus at around 9 months, and for vomiting at around 6 to 7 months.
 
If the patient vomits after taking a dose of trial treatment they should be advised to resume treatment at the next scheduled dose
 
	
	
 
No routine prophylactic anti-emetic treatment is required at the start of trial treatment, however patients should receive appropriate anti-emetic treatment at the first onset of nausea or vomiting and as required thereafter, in accordance with local treatment practice guidelines. Alternatively, olaparib tablets can be taken with a light meal/snack (i.e. 2 pieces of toast or a couple of biscuits). As per international guidance on anti-emetic use in cancer patients (ESMO, NCCN), generally a single agent antiemetic should be considered (e.g. dopamine receptor antagonist, antihistamines or dexamethasone).
 
	
Diarrhoea	• Loperamide 4mg should be administered at the first onset of diarrhoea and then 2mg every 2 hours until diarrhoea-free for at least 12 hours. The first dose of loperamide could be lowered to 2mg if the diarrhoea is recurrent and if, in the opinion of the Investigator, the diarrhoea is not severe.	

Toxicity	Action
Myelodysplastic syndrome (MDS)/Acute Myeloid Leukaemia (AML) NB. MDS/AML are	
 
Patients should be instructed to notify the Investigator or research staff of the occurrence of bloody or black stools, symptoms of dehydration, fever, inability to take liquids by mouth, and inability to control diarrhoea within 24 hours of using loperamide or other prescribed anti diarrhoeal medications.
 
If diarrhoea is severe (i.e., requiring intravenous rehydration) and/or associated with fever or severe neutropenia (Grade 3 or 4), broad-spectrum antibiotics must be prescribed. Patients with severe diarrhoea or any diarrhoea associated with severe nausea or vomiting should be hospitalised for intravenous hydration and correction of electrolyte imbalances.
 
Olaparib treatment should be discontinued if the diagnosis of MDS and/or AML is confirmed and the patient should be treated appropriately.
 
Development of a confirmed MDS and/or AML whilst on trial treatment with olaparib or following treatment discontinuation should be reported as an AESI, please refer to Section 16 for further information.
 

important potential risks for olaparib	
Renal impairment	
 
If creatinine increases to Grade ≥2, creatinine clearance should be calculated by Cockcroft and Gault equation (see Appendix 4). If calculated creatinine clearance is >51 ml/min treatment should be continued at the current dose.
 
A dose reduction is recommended for patients who develop moderate renal impairment (calculated creatinine clearance by Cockcroft-Gault equation of between 31 and 50 ml/min) for any reason during trial treatment. The dose of olaparib should be reduced to 200mg BD.
 
Because the creatinine clearance determination is only an estimate of renal function, in instances where the creatinine clearance falls to between 31 and 50 ml/min, the Investigator should use their discretion in determining whether a dose change or discontinuation of trial treatment is warranted.
 
Caution should be used in patients with a creatinine clearance less than 30ml/min as safety and efficacy have not been evaluated in this population.
 
The safety and efficacy of trial treatment has not been evaluated in patients with severe renal impairment (creatinine clearance ≤30 ml/min) or end-stage renal disease; if patients develop severe impairment or end stage disease it is recommended that all trial treatment be discontinued.
 

Hepatic toxicity	Please refer to Table C4 for hepatic toxicity management guidelines.

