### 24.4. Part 1 Olaparib: Permitted Concomitant Therapy

Patients who are receiving neoadjuvant pembrolizumab as SOC can continue this treatment during Part 1 of the trial. All other medication considered necessary for the participants' welfare and which is not expected to interfere with the evaluation of the trial treatment may be given at the discretion of the investigator. All concomitant medications must be recorded in the patient's notes, as well as the appropriate eCRF pages within the clinical database.

The use of any natural/herbal products or other traditional remedies should be discouraged, but use of these products, as well as use of all vitamins, nutritional supplements, and all other concomitant medications must be recorded in the eCRF.

Bisphosphonates, RANK ligand antagonists (e.g. denosumab) and blood transfusions should be given as required at the discretion of the Investigator.

Patients may take corticosteroids but increased vigilance is recommended on electrolyte and glucose levels.

Patients who require anti-coagulation during trial treatment should start on LMWH.

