#### PLEASE REFER TO APPENDIX 6 FOR PROHIBITED CONCURRENT MEDICATIONS FOR OLAPARIB.

It is recommended that known potent inhibitors/inducers of CYP3A are not co-administered with olaparib. Please see Appendix 6 for details. The required washout period prior to commencing trial treatment is 5 weeks for known strong or moderate CYP3A inhibitors or inducers. Please refer to Section 8.1.2 Trial Entry Exclusion Criteria for further information.

Caution should be exercised when substrates of CYP3A4 or UGT1A1 are combined with olaparib, in particular those with a narrow therapeutic margin. Caution should be exercise if olaparib is administered in combination with P-gp inhibitors which may increase exposure to olaparib. Caution should be exercised if olaparib is administered in combination with any statin. **Please see Appendix 6 for additional guidance.** 

Based on limited *in vitro* data, olaparib may increase the exposure to substrates of CYP3A4, P-gp, OATP1B1, OCT1, OCT2, OAT3, MATE1 and MATE2K. Based on limited *in vitro* data, olaparib may reduce the exposure to substrates of CYP3A4, CYP1A2, 2B6, 2C9, 2C19 and P-gp. **Please see Appendix 6 for examples of substrates.** 

The efficacy of hormonal contraceptives may be reduced if co-administered with olaparib.

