#### STRONG OR MODERATE CYP3A INDUCERS

Strong (e.g., phenobarbital, phenytoin, rifampicin, rifabutin, rifapentine, carbamazepine, nevirapine, enzalutamide and St John's Wort) and moderate CYP3A inducers (e.g. bosentan, efavirenz, modafinil) of CYP3A should not be taken with olaparib. If the use of any strong or moderate CYP3A inducers are considered necessary for the patient's safety and welfare this could diminish the clinical efficacy of olaparib. If a patient requires use of a strong or moderate CYP3A inducer or inhibitor then they must be monitored carefully for any change in efficacy of olaparib.

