		interactions identified with		
		cyclizine are mainly		
		pharmacodynamic in nature. Listed as a substrate of CYP2D6		
		which shows a 33% increase in		
		concentration in poor		
		metabolisers compared to		
		extensive CYP2D6		
		metabolisers. No treatment		
		restrictions based on the		
		CYP2D6 phenotype of patients		
		identified.		
Dexamethasone	Anti-emetic	Dexamethasone is a	Moderate	Dexamethasone
	(steroid)	moderate inducer of CYP3A4		may induce
		and is sensitive to strong		metabolism of
		inhibitors of CYP3A4.		Olaparib.
		P-glycoprotein inducer		Olaparib is a weak
				inhibitor of CYP3A4
				and may inhibit dexamethasone
				metabolism.
				metabolism.

Granisetron	Anti-emetic	Not identified as a sensitive	Low	Olaparib is a P- glycoprotein inhibitor
	(5-HT3 antagonist)	CYP3A4 or 2D6 substrate. However, no interaction studies have been performed		
Ondansetron	Anti-emetic (5-HT3 antagonist)	CYP3A4 and 2D6 substrate – inhibitors known to reduce clearance of ondansetron	Moderate	Olaparib is a weak inhibitor of CYP3A4
cefuroxime	Anti- infective	These anti-infective agents are primarily cleared by excretion	Low	
Co-amoxiclav	Anti- infective	of unchanged drug in urine. At this time no likelihood of	Low	
flucloxacillin	Anti- infective	interactions has been identified	Low	
gentamycin	Anti- infective		Low	
teicoplanin	Anti- infective		Low	
vancomycin	Anti- infective		Low	
erythromycin	Anti- infective	Has the potential for interaction as it is an inhibitor of CYP3A4 and also a substrate of CYP3A4 affected by strong inhibitors. Inhibits OATP1B1 Inhibits P-glycoprotein		Erythromycin may inhibit Olaparib metabolism Olaparib may inhibit erythromycin metabolism Olaparib inhibits OATP1B1 Olaparib is a P-glycoprotein substrate and inhibitor Current studies recommend combined use with caution
propofol	Induction agent	PK does not appear to be affected by renal and hepatic impairment – no potential for interaction identified.	Low	
atracurium	NMJ block	Metabolised by non-specific plasma cholinesterases and chemical instability (Hofmann elimination) – no potential for interaction identified.	Low	
suxamethonium	NMJ block	Metabolised by plasma cholinesterases – no potential for interaction identified.	Low	

rocuronium	NMJ block	Hepatic clearance. Uncertain Which cytochrome P450's (CYPs) are involved.	Moderate	Uncertain – avoid if possible

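### The Part 2 nausea guidance in 25.2.3 offers dexamethasone, which Appendix 6 classes as a moderate CYP3A4 inducer and Appendix 5 therefore advises against with olaparib; 24.5 separately sends window sites to the wrong appendix for prohibited medications

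*Protocol*

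**What the plan says.** All references are to the protocol.

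- **Section 25.2.3, nausea and vomiting row (Part 2).** Anti-emetics are given from first onset and as needed, and "generally a single agent antiemetic should be considered (e.g. dopamine receptor antagonist, antihistamines or dexamethasone").
- **Appendix 6, Table 2, dexamethasone row.** The drug is a "moderate inducer of CYP3A4" and may induce olaparib metabolism. The likelihood of a clinically important interaction is rated moderate. No instruction follows.
- **Appendix 5, inducers.** Strong agents and "moderate CYP3A inducers (e.g. bosentan, efavirenz, modafinil) of CYP3A should not be taken with olaparib". If one is considered necessary for the patient's "safety and welfare this could diminish the clinical efficacy of olaparib", and the patient must be monitored for a change in efficacy.
- **Sections 24.4 (window) and 25.2.7 (Part 2).** "Patients may take corticosteroids but increased vigilance is recommended on electrolyte and glucose levels". Both sections also limit discretionary medication in general to what is "not expected to interfere with the evaluation of the trial treatment".
- **Section 24.5 (window).** "PLEASE REFER TO APPENDIX 6 FOR PROHIBITED CONCURRENT MEDICATIONS FOR OLAPARIB". The body text adds: "It is recommended that known potent inhibitors/inducers of CYP3A are not co-administered with olaparib". It also sets a 5-week washout before treatment for strong or moderate CYP3A inhibitors or inducers. The parallel Part 2 text in Section 25.2.8 cites Appendix 5 in the same places.

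**The concern.** A site that follows the nausea row can prescribe, as a routine option, a drug that the protocol elsewhere says may lower olaparib exposure and belongs to a class to be avoided. The row carries no necessity test, no monitoring and no cross-reference, and it lists two other anti-emetic classes beside dexamethasone.

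The corticosteroid permission in 24.4 matters more for the trial's main question, because it covers the 14-day window that yields the paired biopsies and plasma for the primary endpoint. Evaluability under Section 24.1.2 rests on doses taken (at least 80%, plus both Day 14 doses). A dose count would not reveal exposure lost through induced metabolism. The pointer error falls in the same part of the protocol: a window site looking up what is prohibited is sent to the anaesthetic-interaction appendix.

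**Working it through.** The protocol gives no figure to reproduce, so the check sets the passages side by side.

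**Step 1: is there a conflict on dexamethasone?**

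| Place | What it does |
|---|---|
| Appendix 6, Table 2 | Classes dexamethasone as a moderate CYP3A4 inducer that may act on olaparib |
| Appendix 5 | Advises against moderate inducers with olaparib, save for necessity with monitoring |
| 25.2.3 nausea row | Offers dexamethasone as an ordinary example |
| 24.4, 25.2.7 | Permit corticosteroids; cautions on electrolytes and glucose only |

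The Appendix 5 drug names are introduced as examples, so omitting dexamethasone there does not exempt it. Once the Appendix 6 classification is applied, the nausea row and the Appendix 5 rule do not fit together unless necessity is invoked, and the row does not invoke it.

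**Step 2: do other clauses remove the conflict?** The general clause in 24.4 and 25.2.7 about interference does not identify dexamethasone, and corticosteroids are then permitted expressly. Section 25.3.8 limits systemic steroids in patients on durvalumab, but because of immunosuppression. It does not apply to the window or to Part 2 patients on olaparib alone (Section 12.1.3).

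**Step 3: the four appendix pointers in 24.5.** All four name Appendix 6; their counterparts in 25.2.8 all name Appendix 5.

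| Pointer in 24.5 | Where the content is | Result |
|---|---|---|
| Prohibited medications | Appendix 5 | Wrong |
| Details on CYP3A inhibitors/inducers | Appendix 5 | Wrong |
| Additional guidance on substrates, P-gp inhibitors, statins | Both; the brochure extract in Appendix 6 has CYP3A4 and UGT1A1 cautions | Partly served |
| Examples of substrates | Both; Appendix 5 is fuller, but only Appendix 6 gives UGT1A1 examples | Partly served |

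The on-treatment rule for moderate inducers stands only in Appendix 5, because the body text of 24.5 and 25.2.8 advises against potent agents. Section 24 never cites Appendix 5.

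**Step 4: reach, as a ceiling.** Section 5.1 gives maxima of 15 for cohort E, 8 for F and 15 for G.

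- Window (24.4 and 24.5): 15 + 8 + 15 = 38 evaluable patients.
- Part 2 (nausea row and 25.2.7): 8 + 15 = 23 patients.

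The share who would receive dexamethasone is not stated. Taking 0 to 100% as an assumption gives 0 to 38 in the window and 0 to 23 in Part 2, which is a bound and not an estimate.

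**Step 5: would naming dexamethasone as an inducer cause a new problem?** Section 8.1.2 requires a 5-week washout for moderate inducers. Section 3.1 lets the window open 3 weeks after day 1 of the final chemotherapy cycle. If dexamethasone was given on that day (an assumption; the protocol does not say), the washout would run 5 − 3 = 2 weeks past the earliest opening. A correction without an exemption could therefore delay or exclude patients.

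**The case against.** The strongest reply is that the conflict is inferred. None of the inducer lists (Sections 5.3.2 and 8.1.2, Appendix 5) names dexamethasone. The Appendix 6 row gives no instruction to avoid it, whereas the same table does so for rocuronium and vecuronium. The texts that deal specifically with dexamethasone or corticosteroids permit use, and Appendix 5 is a general advisory rule with an allowance for necessity. This stands as far as it goes: a reader might infer that the protocol prohibits dexamethasone, and it does not. What remains is that the nausea row offers it without the necessity and monitoring that Appendix 5 attaches to its class.

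A second reply concerns 24.5. A reader might infer that all four pointers are simply wrong. The documents do not support that, since Appendix 6 reproduces interaction text from the brochure that partly serves two of them. Appendix 6 also holds the only warning about dexamethasone, so moving every pointer to Appendix 5 would take window readers away from it. Section 24.5 also refers to the entry criteria in 8.1.2, which put moderate inducers before the site, though only as a restriction before treatment. This reply narrows the error to two wrong pointers and two incomplete ones.

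Third, no consequence is demonstrated. Section 24 does not suggest dexamethasone, and the Day 14 biopsy normally precedes surgery, so anaesthetic use normally falls after the endpoint sample. The nausea row concerns Part 2, which Section 17.1.2 describes as exploratory and descriptive, and the durvalumab steroid limits narrow its practical scope. All of this stands.

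**Conclusion.** The point holds as an internal inconsistency that warrants a minor-to-moderate wording correction. The Part 2 nausea row conflicts with the combined reading of Appendices 5 and 6; 24.4 and 25.2.7 omit the induction caution; and 24.5 misdirects window sites for prohibited medications and co-administration details.

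The ceiling is 38 window patients and 23 in Part 2. The conclusion rests on the protocol's own classification of dexamethasone and on reading the Appendix 5 drug names as examples. A reader might go further and infer that the window endpoint is biased or that the cohort G decision could change. The protocol does not support that: it gives neither the extent of dexamethasone use nor the size of any loss of olaparib exposure.

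**What to change.** - **25.2.3, nausea row:** delete dexamethasone from the examples; the two other classes remain.
- **24.4 and 25.2.7:** add that systemic dexamethasone during olaparib is to be used only if necessary under Appendix 5.
- **24.5:** point the prohibited-medication and details references to Appendix 5, and the additional-guidance and substrate references to both Appendices 5 and 6. Keep Appendix 6 for the Day 14 anaesthetic review.
- **Appendix 5:** name dexamethasone among the moderate inducers, with an explicit exemption from the 5-week washout for anti-emetic or pre-medication use with the final chemotherapy cycle. Cross-refer to the exemption from 8.1.2, where the washout is imposed.

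The cost is a wording amendment and one fewer named anti-emetic. No data, visits or analyses are added. The washout exemption should go in together with the naming; otherwise the correction could affect eligibility or timing.

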### 12.1. Eligibility Criteria for Trial Treatment in Part 2 - Cohorts F & G only

As all patients receive olaparib during the post-neoadjuvant treatment and pre-surgical 14-day WOP, fulfilment of eligibility criteria for olaparib treatment is confirmed at the time of Trial Entry. To determine eligibility for further olaparib trial treatment in Part 2, pre-treatment assessments will include repeat physical examination and assessments of vital signs, ECOG performance status, and safety bloods as detailed in Section 13.1. These pre-treatment assessments should be used to determine fulfilment of the eligibility criteria for further olaparib treatment in Part 2 included in Section 12.1.1 below. Any patients who experienced unacceptable toxicity as judged by the investigator and/or discontinued olaparib treatment during the WOP should not be invited to consent to further trial treatment in Part 2, and should receive SOC treatment of Physician's Choice and followed up as described in Section 14.

IRAS Project Number: 249774

Patients who remain eligible for further olaparib treatment in Part 2, must fulfil the exclusion criteria for durvalumab listed below (Section 12.1.2) to receive olaparib and durvalumab combination therapy otherwise they will receive olaparib alone (Section 12.1.3):

### 12.1.1. Inclusion Criteria for trial treatment in Part 2

- 1. Eastern Oncology Cooperative Group (ECOG) performance status 0-1;
- 2. Confirmation of residual disease following primary surgery as per local pathology reporting;
- 3. Patients must have adequate haematological, renal and hepatic function as defined by:
  - Haemoglobin (Hb) ≥ 10 g/dL (≥ 100 g/L)
  - Absolute neutrophil count (ANC)  $\geq 1500/\text{mm}^3$  ( $\geq 1.5 \times 10^9/\text{L}$ )
  - Platelet count ≥100,000/mm³ (≥ 100 x 109/L)
  - Total bilirubin ≤ 1.5 x institutional upper limit of normal (ULN)
  - Aspartate aminotransferase (AST) (Serum Glutamic Oxaloacetic Transaminase (SGOT)) / Alanine aminotransferase (ALT) (Serum Glutamic Pyruvate Transaminase (SGPT))  $\leq$  2.5 x institutional ULN
  - Calculated creatinine clearance ≥51 mL/min using the Cockcroft-Gault equation (please refer to Appendix 4) or based on a 24 hour urine test or another validated test as per local practice

### 12.1.2. Exclusion Criteria for durvalumab treatment in Part 2

- 1. Body weight  $\leq$  30kg.
- 2. Patients who have received prior pembrolizumab:

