### 13.2. PART 2 On-Treatment Assessments Cycle 2, Day 1 Pre-Treatment

The following assessments should be performed as close to as possible and within 3 days prior to treatment administration:

- Physical examination and vital signs (including weight, blood pressure, heart rate, temperature)
- ECOG performance status
- Dosing compliance
- Review of concomitant medications
- Safety bloods: Haematology full blood count, white cell count with differential and ANC, prothrombin time and international normalised ratio (INR); Biochemistry sodium, potassium, calcium, magnesium, ALT, gamma-glutamyl transferase (GGT), bilirubin, albumin, creatinine, alkaline phosphatase, glucose, urea. In addition for patients receiving durvalumab: TSH
- ECG
- Review of AEs
- Pregnancy test for women of childbearing potential

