### 13.3. PART 2 On-Treatment Assessments Cycle 3 Onwards, Day 1 Pre-Treatment

The following assessments should be performed as close to as possible and within 3 days prior to treatment administration:

- Physical examination and vital signs (including weight, blood pressure, heart rate, temperature)
- ECOG performance status
- Dosing compliance
- Review of concomitant medications
- Safety bloods: Haematology full blood count, white cell count with differential and ANC, prothrombin time and international normalised ratio (INR); Biochemistry sodium, potassium, calcium, magnesium, ALT, gamma-glutamyl transferase (GGT), bilirubin, albumin, creatinine, alkaline phosphatase, glucose, urea. In addition for patients receiving durvalumab: TSH
- ECG
- Review of AEs
- Pregnancy test for women of childbearing potential

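### Part 2 olaparib: the renal dose-reduction advice depends on calculated clearance, but no on-treatment calculation is required until creatinine reaches Grade 2

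*Protocol*

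**What the plan says.** The renal-impairment row of the non-haematological toxicity table (Protocol 25.2.3) holds these rules:

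- **When to calculate.** "If creatinine increases to Grade ≥2, creatinine clearance should be calculated by Cockcroft and Gault equation (see Appendix 4". If the result is above a stated value, the dose is kept: the sign > is followed by "51 ml/min treatment should be continued at the current dose".
- **When to reduce.** A reduction to 200 mg twice daily is recommended if calculated clearance is "between 31 and 50 ml/min) for any reason during trial treatment".
- **Discretion.** For the same 31 to 50 band, the row notes that clearance is only an estimate and leaves a dose change or discontinuation to the investigator's judgement.
- **Low values.** "Caution should be used in patients with a creatinine clearance less than 30ml/min". The next bullet covers 30 ml/min or less, where "it is recommended that all trial treatment be discontinued".

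The entry criterion for Part 2 treatment (12.1.1) is "Calculated creatinine clearance ≥51 mL/min using the Cockcroft-Gault equation", with a 24-hour urine test or another locally validated test as alternatives. From Cycle 2, sections 13.2 and 13.3 introduce the visit list with "The following assessments should be performed as close to as possible and within 3 days prior to treatment administration". That list includes weight, and its biochemistry panel ends "bilirubin, albumin, creatinine, alkaline phosphatase, glucose, urea". Clearance is not on it, nor in the footnotes to 13.8. The criteria in 25.2.2 for starting a cycle are blood counts only.

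**The concern.** The reduction rule applies to any patient in the 31 to 50 band, whatever the cause. The instruction that would reveal membership of the band applies only once creatinine has reached Grade 2. A site that follows the text exactly could therefore hold the creatinine and weight that place a patient in the band and never be told to combine them.

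Two routes lead there: a creatinine rise that stays below Grade 2, and weight loss, which a creatinine trigger cannot detect at all. Both are plausible on this drug. Section 1.2 lists raised blood creatinine, decreased appetite, nausea, vomiting and diarrhoea among the events associated with olaparib.

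What is at stake is Part 2 safety management: the recommendation and the discretion written into the row cannot be exercised on a value nobody has worked out.

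**Working it through.** **Inputs.** Appendix 4 formula for women; entry minimum 51 ml/min (12.1.1); reduction band 31 to 50 ml/min (25.2.3); at most 23 treated patients in Part 2 (5.1: 8 in Cohort F + 15 in Cohort G). The protocol states no figure of its own on this point, so there is none to reproduce.

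**Formula.** Clearance = (140 − age) × kg × 1.04 / creatinine (µmol/L). It is proportional to weight and inversely proportional to creatinine. From a starting clearance c0:

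- creatinine rise that brings clearance to 50 = c0/50 − 1
- weight loss that brings clearance to 50 = 1 − 50/c0

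| Clearance at entry | Creatinine rise alone | Weight loss alone |
|---|---|---|
| 51 | 51/50 − 1 = 2.0% | 1 − 50/51 = 2.0% |
| 55 | 55/50 − 1 = 10% | 1 − 50/55 = 9.1% |
| 60 | 60/50 − 1 = 20% | 1 − 50/60 = 16.7% |

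**Example at the entry minimum.** Woman aged 60, 65 kg, creatinine 106 µmol/L: 80 × 65 × 1.04 = 5408, and 5408/106 = 51.0. Clearance reaches 50 at 5408/50 = 108.2 µmol/L. With creatinine unchanged it reaches 50 at 50 × 106/(80 × 1.04) = 63.7 kg, a loss of 1.3 kg.

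**Example further away.** Woman aged 60, 60 kg: 80 × 60 × 1.04 = 4992. At 80 µmol/L clearance is 62.4; at 110 µmol/L it is 45.4, after a 1.375-fold rise.

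**Dependence on the Grade 2 cut-off.** The protocol grades by CTCAE v5.0 but does not print the creatinine cut-offs, so these are assumptions. If Grade 2 begins at k times the patient's baseline, everyone entering between 51 and 50 × k ml/min reaches 50 before or at the trigger:

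- k = 1.1: entry 51 to 55
- k = 1.25: entry 51 to 62.5
- k = 1.5: entry 51 to 75
- k = 2.0: entry 51 to 100

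For entry at 51 the gap closes only if k is 51/50 = 1.02 or less. With a fixed cut-off of 120 to 150 µmol/L instead, the first example patient is at 5408/120 = 45.1 to 5408/150 = 36.1 ml/min when the calculation is first required. No choice of cut-off covers weight loss.

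**Search for another prompt.** Section 16.2 treats laboratory findings as reportable events from Grade 2 upwards, so it does not catch a lower rise. The nephritis guidance in Appendix 7 applies to patients on durvalumab. It names reduced creatinine clearance as one example of a sign to watch and asks for weekly creatinine at Grade 1, but it requires no calculation and sets no olaparib dose. Patients on olaparib monotherapy (12.1.3) do not have that partial cover. No other section requires an on-treatment calculation.

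**The case against.** The strongest reply is that nothing here conflicts. A compulsory calculation at Grade 2 can stand beside a broader reduction rule, earlier calculation is not forbidden, and creatinine and weight are in front of the investigator at every cycle. That stands: a reader might infer that the row contradicts itself, and it does not. What remains is that a row naming one specific trigger invites sites to wait for it, and the discretion presupposes a known clearance.

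A reader might also infer that an undetected patient is overdosed, at 600 rather than 400 mg a day. The row does not support that. Reduction is recommended, not required, and remaining on 300 mg twice daily after review is a permitted outcome. What is lost is the prompt to decide.

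Nor are monotherapy patients without any renal safeguard. They have creatinine and weight at each cycle, reporting of Grade 2 laboratory findings (16.2), interruption at Grade 3 or above (25.2.4) and discontinuation on investigator judgement (25.1.2).

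The 2% figure describes a patient at the exact entry minimum crossing one unit of a value the protocol calls an estimate. The larger falls rest on assumed cut-offs, so they cannot carry the point.

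Finally, a later trigger may protect against unnecessary reductions. Appendix 5 lists serum creatinine under OCT2, and Appendix 6 says olaparib may inhibit that and other renal transporters, so some calculated falls may not be lost function. This argues for keeping discretion, but not for leaving clearance uncalculated.

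**Conclusion.** The point holds as a gap in detection. A patient who enters near 51 ml/min can be in the 31 to 50 band after a small creatinine rise or weight loss, with no instruction that would lead the investigator to apply the recommendation or the discretion. For entry at 51 this would fail only if Grade 2 began at a rise of about 2%, and even then weight loss would go unseen.

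The size is modest. At most 23 patients are concerned, mainly those on olaparib monotherapy. The numbers entering near 51 or receiving monotherapy are unknown. Part 2 is exploratory and descriptive (17.1.2), and no primary endpoint is affected. It is worth correcting because the correction is cheap.

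Two wording points in the row are minor. The continue rule excludes 51, the value at which entry is allowed, so exactly 51 has no stated action. A reader might take the caution below 30 and the advice to stop at 30 or below as conflicting; the first is merely redundant beside the second.

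**What to change.** Require the site to calculate Cockcroft-Gault clearance before dosing at each cycle from Cycle 2, whatever the creatinine grade, from age and the creatinine and weight already collected within 3 days before treatment. Cycle 1 is covered by the entry criterion. Change >51 to ≥51 in the continue rule to match 12.1.1; read in whole ml/min, the bands then meet.

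Keep the 31 to 50 recommendation, the investigator discretion and the advice to stop at 30 or below unchanged. Do not make reduction the default and do not widen the band. Under 25.2.2 a reduction is not reversed, and 200 mg twice daily is already the second reduction level, with discontinuation next. This weighs most in Cohort F, for which section 1.2 cites proven benefit.

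**Cost.** One table row and the two visit lists are reworded, and the site makes one calculation per cycle: at most 12 per patient (Cycles 2 to 13), or 12 × 23 = 276 in all. No visit or routine test is added.

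**Downside.** Some flagged falls may reflect blocked creatinine transport rather than lost function. A repeat creatinine taken on olaparib would not remove that effect. The retained discretion limits unnecessary reductions, and the row could name as an option the 24-hour urine or other validated local test that 12.1.1 already allows.
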